STUDY OBJECTIVES:

The primary objective of this revised protocol will be to examine the safety and efficacy of IVIG 2gm/kg (maximum dose 140g) given on day#0 & day #30 plus Rituximab 1gm given on day#15. Transplanted patients will receive additional doses of Rituximab 1gm at 3 months post-transplant if DSA levels remain or become +. OR at 6M if de novo DSA occur. All transplanted patients who remain DSA-, will not receive additional Rituximab. All transplanted patients will have a protocol biopsy at 12 months.

This trial is designed to determine if Rituximab + IVIG is an effective and safe desensitization protocol and if DSAs persisting or arising at 3M and 6M post-transplant can be effectively reduced by additional doses of Rituximab. This should be reflected in reduced rates of TG for Rituximab-treated patients. This is the PRIMARY END POINT. Secondary end points include and will be evaluated based on time line in appendix A:

- Renal allograft survival at 12M

- Reduction in anti-HLA antibodies (class I/II)
- Recipient survival at 12M
- The number of acute rejection episodes
- Rates of serious infectious complications (i.e., serious infections requiring hospitalizations and/or i.v. antibiotics)
- Adverse events, toxicity assessments
- Abnormal laboratory studies: Hematology, Chemistry, Liver Function, and research tests on study
- Clinical significant abnormalities in physical examination, vital signs, weight, ECG or Chest X-ray on study
- Serial donor-specific antibody assessments
- Pre & Post-transplant determinations of CD4+/CD25+FoxP3+CD127+ & Th17 cell populations (Cedars-Sinai Patients Only).
- Pre & Post-Transplant determinations of CD19+, CD38+, CD27+ cells (Cedars-Sinai Patients Only).
- Post-Transplant biopsy at T0 and T12M assessed by Banff Criteria.
- HACA determinations at serial intervals

PRELIMINARY DATA

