Effects of Desensitization on cPRA, Crossmatch and DSA Results

The effect of desensitization on flow cytometry PRA determinations were performed on a subset of 39 HS patients. This data show that the mean pre-treatment class I PRA was 79.7 ± 25.6 % vs post-treatment 67.1 ± 28.6 %, (p=0.0001). The mean pre-treatment class II PRA was 59.7 ± 29.2 vs. post-treatment 49.7 ± 27.8 , (p=0.01). This reduction is less than reported previously (2). Reasons for this difference include a change in technique from cytotoxicity-based PRA determinations to solid phase antibody testing using flow cytometry and luminex bead technologies. Both cytotoxicity and solid phase assays are susceptible to interference from IVIG but only for a period of less than a week after IVIG administration. Twenty five percent of treated patients experienced a reduction in flow cytometry PRA of 25% or greater. Analyses of transplantation and outcomes by flow cytometry PRA (Class I or II) and donor type are shown in figure 1. Seventy five percent of patients had flow cytometry PRA \geq 80% (19LD/38DD) before desensitization. These patients also experienced more ABMR episodes. A significant reduction was seen in FCMX positivity against donor T-cells for patients receiving LD and DD transplants after desensitization (Fig 2A & 2B). Figure 2A shows the MCS results for T-cell FCMXs for all 31 individual LD recipients were available. Figure 2A shows the mean values for MCS pre-treatment and at transplant. Briefly, T-cell FCMX were significantly reduced from 183 ± 98 MCS prior to therapy to 68 ± 58 MCS at time of transplant (p<0.000006). T-cell FCMX data for DD recipients pre-treatment and at transplant are shown in figure 2B. Briefly, a significant reduction in mean T-cell FCMX was seen after desensitization in DD recipients (162 ± 41 MCS pre-treatment vs. 125 ± 49 MCS at transplant {p=0.05}). Table 3 shows rejection type and graft loss by DSA.

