This single (or multiple)-center, Phase I/II, exploratory study will use an open label design. The revision of this protocol is attributed to the failure of the placebo controlled protocol which showed a significant increase in SAEs in the IVIG + placebo group (3 antibody-mediated rejection episodes of 5 transplanted compared with 0 ABMR episodes in the IVIG + Rituximab group, $p=0.038$). The original study was put on hold and this iteration represents a redesign of the protocol to investigate the optimal dosing of Rituximab for desensitization and for modification of DSA levels post-transplant. The trial will examine the safety and efficacy of human polyclonal IgIV 10%, when given at [2.0 gm/kgx2], + Rituximab 1gm to reduce DSA to a level that is permissive for DD transplantation in 75 subjects (adults only ages ≥ 18 yrs) who are highly-HLA sensitized and are awaiting DD kidney transplant. Once transplant offers are entertained, a donor-specific crossmatch will be performed to detect anti-HLA antibodies which are associated with acute rejection or graft loss. (These anti-HLA antibodies may result naturally or from some previous pregnancy, transfusions, or prior transplants). If acceptable crossmatches and DSA levels are seen, the patients will proceed to DD transplantation. Patients receiving transplants will receive an additional dose of IVIG at transplantation (within 10 days) and will receive additional doses of Rituximab 1g) at 3M post-transplant if they remain or develop DSAs. OR at 6M if de novo DSAs occur (Fig 5 & 6). Patients who are desensitized and not transplanted within 9 M after desensitization will have completed the study and can be treated as best judged by the participating center. The protocol is shown in Figure 4 below.

[figure not shown]

Figure 4: Study Protocol for revised IVIG + Rituximab Study.

The decision to accept a DD transplant will rest entirely with the participating transplant center.

The subjects will be followed to determine the proportion who receive a transplant within 9M of completion of the infusions. In addition we will assess the transplanted patients to determine the number who sustain a viable and functioning kidney allograft for 12 months at which time a repeat study biopsy will be performed. All subjects will be evaluated on an intent-to-treat basis. The subject accrual rate will be limited to no more than five subjects per month in the initial three months to assure safety to all subjects.

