1.3 Planned Efficacy Evaluations

The efficacy end points will be evaluated after all 75 patients have been enrolled into the trial. We plan to evaluate rates of deceased donor transplantation as well as conversion rate of DSA and rates of ABMR in those transplanted. The efficacy of the proposed combination of IVIG + Rituximab will be determined by the statistical methods. These evaluations will be carried out in concert with our safety monitoring that is outlined in section 9.0. The appropriate stopping points and re-evaluation points are described there as well.

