1.3.2 Secondary Efficacy Variables

In addition to the primary efficacy variables, we will evaluate a number of secondary efficacy variables. These include donor-specific antibody testing, patient and graft survival, infectious complications, immunologic testing, protocol biopsies and rates of allograft rejection. These end points are outlined in section 2.0 and Appendix A. Data will be analyzed in the treatment group.

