1.3.3 Methods of Analysis

Rituximab + IVIG for Desensitization

We aim to recruit 75 HS patients on the basis of a clinically relevant increase in the absolute rate of transplantation for highly-HLA sensitized deceased donor recipients of approximately 50 percentage points between the two groups during 9 months of follow-up, with an estimated event rate of 15% in the control UNOS study group. We determined that this number of patients would provide the study with a power of 95%, with a two-sided type I error of 5% and a nonadherence or loss to follow up rate of 5(or 10)%. A transplant rate of 60-70% in the intervention limb is based on our experience with desensitization in the recent years (49, 113, 131). All analyses shall be performed on the basis of the intention-to-treat principle. Patients that were transplanted outside of the study will be included in the analysis.

We shall compare the proportions of patients in the treatment group compared to the UNOS control group using time-to-event analysis with respect to outcomes such as the primary outcome (rate of transplantation) and certain secondary outcomes (such as recipient and graft survival, occurrence of rejection in the treatment group only). These outcomes shall be analyzed with the use of the log-rank test. Cox proportional-hazards regression shall be used to obtain unadjusted hazard ratios and to adjust for significant stratifying variables and to test for effect modification in all secondary analyses. Data from patients who are lost to follow-up shall be regarded as censored at the time of the last contact. Data from patients who do not receive transplantation shall be censored at end of 9 months post desensitization. We shall use Kaplan–Meier estimates of the proportion of patients with the above listed outcomes. We shall calculate the number of patients who would need to be desensitized to allow one deceased donor renal transplant from the hazard ratio and its 95% confidence interval.

For other outcomes, the Chi square or Fischer exact test shall be used if the variable is categorical, and the t-test or signed rank test if it is continuous variable.

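### Section 1.3.3 names only independent-sample tests for categorical outcomes, but change in DSA status is a within-patient comparison, so before/after p-values under that rule would be invalid

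*Combined protocol and SAP*

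**What the plan says.** Section 1.3.3 (Methods of Analysis) assigns the transplant rate, survival and rejection to time-to-event methods. Everything else falls under one sentence: "For other outcomes, the Chi square or Fischer exact test shall be used if the variable is categorical". For continuous outcomes the same sentence offers a t-test, without saying whether it is paired, or else the signed rank test. No paired categorical test is named anywhere in the plan.

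The outcomes that this sentence has to cover include within-patient changes. Section 1.3 (Planned Efficacy Evaluations) lists "conversion rate of DSA and rates of ABMR in those transplanted". The Study Objectives ask whether DSAs present at 3 and 6 months after transplant fall after further rituximab. They also list reduction in anti-HLA antibodies and "Serial donor-specific antibody assessments" as secondary end points. Section 1.3.2, which names donor-specific antibody testing among the secondary efficacy variables, adds: "Data will be analyzed in the treatment group". The UNOS comparison concerns the transplant rate; no DSA data from UNOS patients are planned.

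**The concern.** With one treated group and no external DSA data, the comparator for a change in DSA status is the same patient at another time. Chi-square and Fisher's exact test treat the before and after columns as two separate sets of patients. They use only the two marginal counts and discard who changed. The variance they assume for the difference is therefore wrong whenever the two readings on a patient are correlated, as antibody readings normally are.

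At stake is the test of whether treatment lowers DSA. This is a secondary outcome, but also the mechanism that the hypothesis proposes. A real reduction could be declared non-significant, or in some configurations a weak one significant, because of the choice of test.

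**Working it through.** The plan states no figure for this analysis, so there is none to reproduce. The documents give no paired DSA counts either, so the counts below are assumptions and a range of pairings is shown.

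**Inputs.** n=45 transplanted patients, from 60% (the lower transplant rate assumed in Section 1.1) × 75 enrolled. Assumed: 36 DSA-positive before, 28 after. Two-sided 5% level, as the plan states. Let b be the number losing DSA and c the number gaining it, so b − c = 8.

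**Unpaired tests.** Pooled proportion 64/90 = 0.711. SE = √(0.711 × 0.289 × 2/45) = 0.0956. z = (8/45)/0.0956 = 1.86, p=0.063. Fisher gives p=0.103. Neither depends on b and c beyond their difference.

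**Exact McNemar.** p = 2 × P(X ≤ c), with X ~ Binomial(b + c, ½). The within-patient correlation is phi = [(36 − b)(9 − c) − bc]/√(36 × 9 × 28 × 17), with denominator 392.7.

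| Lost/gained | phi | Exact McNemar p |
|---|---|---|
| 8/0 | 252/392.7 = 0.64 | 2 × 1/256 = 0.008 |
| 10/2 | 162/392.7 = 0.41 | 2 × 79/4,096 = 0.039 |
| 12/4 | 72/392.7 = 0.18 | 2 × 2,517/65,536 = 0.077 |
| 15/7 | −63/392.7 = −0.16 | 2 × 280,600/4,194,304 = 0.134 |

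The same margins thus support p-values from 0.008 to 0.134, while chi-square always returns 0.063. The 8/0 row is the most extreme pairing that these margins allow. At 12/4 the exact test exceeds chi-square mainly because it is discrete: large-sample McNemar gives z = 8/√16 = 2.0, p=0.046.

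**General size of the error.** With equal before and after rates p, the difference has variance 2p(1 − p)(1 − ρ)/n, where ρ is the within-patient correlation. Chi-square assumes 2p(1 − p)/n. Its real type I error is then about 2[1 − Φ(1.96/√(1 − ρ))]: 1.9% at ρ=0.3, 0.6% at ρ=0.5 and 7.4% at ρ=−0.2. Simulation (100,000 trials per setting, n=45 and 75) agrees; large-sample McNemar stayed between 4.2% and 5.4%. For a fall from 60% to 45% positive with n=45 and ρ=0.5, simulated power was 21% for chi-square and 49% for McNemar.

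**All patients positive at the start.** Take 45 falling to 40 of 45. Pooled proportion 85/90 = 0.944; z = (5/45)/√(0.944 × 0.056 × 2/45) = 2.30; chi-square p=0.021. Exact McNemar: 2 × (1/2)^5 = 0.063. Here the unpaired p is the smaller one. Much of that gap is large-sample against exact. Like for like the order is the same but the gap small: 0.021 against 0.025 for large-sample McNemar (z = 5/√5 = 2.24), and 0.056 for Fisher against 0.063.

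**The case against.** The strongest reply is that the plan never says that before/after status will be cross-tabulated and tested with chi-square. The sentence is a generic catch-all, and the tests have proper uses here. Examples are comparisons between different treated patients, such as antibody-mediated rejection by DSA level in Table 3 of the preliminary data. A DSA conversion rate can also be read as a single proportion that needs no two-sample test. All of this stands as a limit on the wording: misuse follows from the rule if it is applied to change in status, but it is not written out. It does not remove the point, because the rule is mandatory and offers no valid test for a within-patient binary change.

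Three stronger readings are tempting, and the documents do not support them.

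- A reader might infer that confidence intervals will be wrong too. Section 1.3.3 asks for 95% intervals for hazard ratios and risk differences, but ties no interval method to chi-square or Fisher. What can be said is that no paired interval is specified.
- A reader might take the preliminary PRA results (39 patients) as proof of the error. An unpaired t-test on the reported class II means and SDs gives t = 10.0/√((29.2² + 27.8²)/39) = 1.55, p=0.13, against a reported 0.01. Class I gives t = 12.6/√((25.6² + 28.6²)/39) = 2.05, p=0.044, against 0.0001. The mismatch suggests the opposite: that the sponsor already analyses continuous change as paired. The signed rank test named in 1.3.3 is also a paired method.
- A reader might infer that serial DSA readings will be pooled as if independent. Nothing in the text proposes this. A mixed model for serial DSA is a reasonable option, but a preference in an exploratory Phase I/II study, not a correction.

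**Conclusion.** The point holds in a limited form. If Section 1.3.3 is followed for change in DSA status, the p-value is invalid. The usual direction is conservative when within-patient correlation is strongly positive, but this is not general. It reverses with negative correlation, and in the example where everyone starts positive. That last case is relevant, since the Study Objectives tie the additional 3-month rituximab dose to persisting or new DSA, so patients followed for its effect start out positive.

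The sizes rest on assumed counts and correlations. They show that the choice of test can move a result across 0.05 in either direction; they do not predict the trial's result. Infection, rejection and survival outcomes are not before/after pairs and are not touched. Neither are the primary transplant-rate analysis and the sample size of 75. It is worth correcting before analysis, because DSA conversion is a named efficacy evaluation and the remedy is almost free.

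**What to change.** Replace the catch-all sentence in 1.3.3 with a rule that separates the two situations:

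- Within-patient binary change between two time points (for example DSA positive or negative): exact McNemar test, with a paired 95% confidence interval for the difference in proportions.
- Where all patients in the analysis start DSA-positive: the proportion converted, with an exact or Wilson 95% interval, and no before/after test.
- Within-patient continuous change: state that the t-test is the paired t-test; the signed rank test can stay as it is.
- Comparisons between different patients: keep chi-square or Fisher's exact test.

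The plan should also name the two time points for each before/after comparison, unless Appendix A already does so. The cost is SAP wording and minor programming. No new data are needed, and neither the sample size nor the primary analysis changes.

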To determine whether the treatment effect varies according to the patients' PRA status, a priori subgroup analysis shall be planned with patients stratified according to the titer of PRA (>80% or <80%), and a test of interaction shall be performed in a Cox model. Post hoc subgroup analyses shall be conducted with the use of other stratifying variables. Treatment effects shall be described in terms of hazard ratios and absolute risk differences with 95% confidence intervals. All P values reported shall be two-sided and adjudged significant if <0.05.

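### Section 1.3.3 calls every reported P value below 0.05 significant, with nothing to separate the primary comparison from secondary endpoints, effect-modification tests and an unstated number of post hoc subgroups

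*Combined protocol and SAP*

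**What the plan says.** The rule is the last sentence of section 1.3.3: "All P values reported shall be two-sided and adjudged significant if <0.05". It has no exceptions. These analyses fall under it:

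- **Primary comparison.** Sections 1.1 and 1.3.1 name deceased-donor transplantation within 9 months of completing treatment, compared with matched patients on the UNOS list.
- **Secondary endpoints.** The Study Objectives section introduces a list with "Secondary end points include and will be evaluated based on time line in appendix A", and 13 bullets follow. Section 1.3.2 condenses the secondary efficacy variables to about six groups and says they are analysed in the treatment group.
- **Effect modification.** Section 1.3.3 uses Cox regression, among other things, "to test for effect modification in all secondary analyses".
- **One a priori subgroup.** PRA above or below 80%, with an interaction test in a Cox model.
- **Post hoc subgroups.** "Post hoc subgroup analyses shall be conducted with the use of other stratifying variables". Neither the variables nor their number is given.

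The document contains no testing order, alpha allocation or multiplicity adjustment, and no statement that secondary P values are nominal. The Study Design section calls the whole study exploratory but does not attach that label to any P value.

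**The concern.** An exploratory study may report as many nominal P values as it likes. This plan goes further and fixes in advance the verdict on each one. A subgroup chosen after the data are seen, on a variable not yet named, is to be called significant by the same rule as the primary comparison.

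What is at stake is how the results are read. A reader of the trial report could not tell which significant findings carry a controlled error rate and which are one hit among many looks. The primary comparison itself is not damaged.

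**Working it through.** **What the plan states.** It gives no overall error rate across endpoints, so there is no such figure to reproduce. Its only error rate is in the sample-size statement of section 1.3.3 ("with a two-sided type I error of 5" percent), which concerns the transplant-rate comparison. The sample size itself rests on precision and reproduces: 0.50 − 1.96 × √(0.25/75) = 0.50 − 0.113 = 0.387, as in section 1.2. Nothing in this point changes the 75.

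**Inputs.** The per-test threshold is 0.05, two-sided (section 1.3.3). The number of tests k is not stated, so three values are assumed:

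- k = 6: one test for each group in section 1.3.2.
- k = 13: one test for each bullet in Study Objectives.
- k = 26: the 13 bullets plus one effect-modification test each. This is a deliberately wide reading.

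**Formula.** With all nulls true and independent tests, P(at least one false positive) = 1 − 0.95^k.

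- k = 6: 1 − 0.735 = 0.265
- k = 13: 1 − 0.513 = 0.487
- k = 26: 1 − 0.264 = 0.736

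Many endpoints are related (DSA, anti-HLA antibodies, rejection, biopsy, graft survival), so independence overstates the figure. Simulating k two-sided z-tests with equal pairwise correlation (200,000 replicates) gives:

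| Tests | Independent | Corr. 0.3 | Corr. 0.5 | Corr. 0.8 |
|---|---|---|---|---|
| 6 | 0.265 | 0.242 | 0.207 | 0.138 |
| 13 | 0.487 | 0.417 | 0.333 | 0.191 |
| 26 | 0.736 | 0.618 | 0.477 | 0.245 |

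Under any dependence, the bound for 13 tests is 13 × 0.05 = 0.65.

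**A narrower count of effect-modification tests.** The sentence concerns Cox regression, so it reaches only time-to-event outcomes. The secondary ones named there are recipient survival, graft survival and rejection. One test for each, added to 13, gives k = 16: 1 − 0.95^16 = 1 − 0.440 = 0.560 under independence. Adding the PRA interaction gives k = 17: 1 − 0.95^17 = 1 − 0.418 = 0.582.

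**What cannot be computed.** Post hoc subgroups have no stated number, so they add an unknown amount to k. In the other direction, bullets that are only listed or tabulated produce no test, and endpoints with real effects cannot yield a false positive.

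**The case against.** The case against this point is substantial, and much of it stands.

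- **A reader might infer that at least one false claim is about as likely as not.** The documents do not support this. The 0.487 needs exactly 13 independent tests, one per bullet, with every null true, and it leaves out the interaction and subgroup tests. Several bullets (adverse events, laboratory abnormalities, examination and ECG findings, HACA) have no stated hypothesis or comparator. An all-null assumption also sits badly with the preliminary data, which report falls in class I and class II PRA (p=0.0001 and p=0.01).
- **A reader might infer that the plan breaks its own 5% error rate.** It does not. That 5% belongs to the sample-size statement for the transplant-rate comparison, and no rate across secondary endpoints is promised.
- **A reader might infer effect-modification tests on all 13 endpoints.** The sentence is about Cox models, so the 26-test figure is an outer illustration.
- **A reader might infer that the plan claims definitive status for every result.** Section 1.2 uses that word to justify 75 patients for the transplant rate, not for secondary or subgroup findings.
- **The plan does have labels.** It distinguishes primary from secondary, and a priori from post hoc.

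Two replies remain. First, those labels have no consequence, because the closing rule gives every category the same verdict. The word exploratory in Study Design does not change that. Second, analysis in the treatment group alone does not remove P values. Antibodies and cell populations are measured before and after transplant, section 1.3.3 assigns other outcomes to chi-square, Fisher, t or signed rank tests, and the preliminary section reports P values for just such before-and-after changes.

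**Conclusion.** The point holds as a reporting flaw in the significance rule, not as a stated probability of error. The rule covers the primary comparison, the secondary endpoints, the Cox effect-modification tests and an open-ended set of post hoc subgroups alike, without multiplicity control or a nominal label.

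Its size is conditional. With all nulls true, the chance of at least one false significant result is about 0.21 for 6 tests at correlation 0.5, 0.33 to 0.49 for 13 tests (correlation 0.5 to independence), and up to about 0.74 for 26 independent tests. These are not limits: stronger correlation, purely descriptive items and real effects lower the figure, and post hoc subgroups raise it. The choice of 6, 13 or 26 tests is an assumption. The conclusion rests on the wording of the rule, not on any one of these numbers.

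**What to change.** Replace the last sentence of section 1.3.3 with:

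> Only the primary comparison is judged significant at two-sided 0.05. Secondary endpoints, the a priori PRA interaction and effect-modification tests are reported as estimates with 95% confidence intervals, and any P values are nominal; post hoc subgroups are labelled hypothesis-generating.

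Before adopting it, the sponsor must settle which comparison is primary. Study Objectives names reduced transplant glomerulopathy, while sections 1.1 and 1.3.1 name deceased-donor transplantation within 9 months. The new sentence should not decide this by default. If both stayed primary and each were tested at 0.05, the chance of a false positive on at least one would be 1 − 0.95² = 0.0975 under independence with both nulls true, so the alpha would also have to be addressed.

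The change needs no further patients or data and removes no analysis. Section 1.3.3 already promises hazard ratios and risk differences with 95% confidence intervals. The downside is that the sponsor gives up nominal significance claims on secondary and subgroup results, including the pre-specified PRA interaction.
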